### For participants with baseline ALT $\geq$ 1.5 X ULN and normal baseline bilirubin:

- Elevation of ALT  $\ge$ 3 X baseline or  $\ge$ 300 U/L (whichever occurs first)
- Elevation of ALT ≥2 X baseline or ≥300 U/L (whichever occurs first) and presence of severe fatigue, nausea, vomiting, right upper quadrant pain
- Elevation of ALP >2 X ULN
- Elevation of TBL >2 X ULN

Baseline ALT is derived from an average of 2 pretreatment ALT measurements at least 2 weeks apart. Elevated baseline is defined as ALT  $\geq$ 1.5 X ULN. In participants with a sizable stable decrease in ALT (>50% of the baseline value) during treatment, a new baseline, corresponding to the ALT nadir, should be established on an individual basis for subsequent determination of a possible DILI signal.

For participants with Gilbert's syndrome, the criterion of elevation of TBL  $\ge 2X$  ULN should be replaced by a doubling of direct bilirubin or increased INR to > 1.5.

If a study participant meets any of the above criteria during the study, liver testing (Section 10.3) should be repeated within 48 to 72 hours including ALT, AST, ALP, TBL, direct bilirubin, gamma-glutamyl transferase, and creatine kinase to confirm the abnormality and to determine if it is increasing or decreasing. If the abnormality persists or worsens, clinical and laboratory monitoring should be initiated by the investigator and in consultation with the study medical

monitor. Monitoring of ALT, AST, TBL, and ALP should continue until levels normalize or return to approximate baseline levels.

Additional safety data should be collected via eCRF if 1 or more of the following conditions occur:

- participant meets any of the above criteria that trigger additional hepatic safety monitoring on 2 or more consecutive blood tests
- participant discontinued from treatment due to a hepatic event or abnormality of liver tests
- hepatic event considered to be an SAE

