# 9.2. Sample Size Determination

Approximately, 196 participants will be randomized to placebo, tirzepatide 5 mg, tirzepatide 10 mg, or tirzepatide 15 mg in a 1:1:1:1 ratio; assuming a 20% dropout rate, this results in approximately 40 completers per arm. Sample size selection is guided by the objective of establishing superiority of each tirzepatide dose to placebo relative to the proportion of participants achieving NASH resolution without worsening of fibrosis at 52 weeks from randomization. The evaluation of superiority to placebo will be conducted for each of the 3 tirzepatide doses at 2-sided significance level of 0.05 using a test of 2 proportions. The tirzepatide group mean response rate is assumed to be 42.5% and the placebo group mean response rate is assumed to be 12.5%. The chosen sample size provides at least 80% power to establish superiority of tirzepatide 5 mg, tirzepatide 10 mg, or tirzepatide 15 mg doses to placebo. No adjustment for multiplicity will be performed.

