1.3. Tertiary/Exploratory Objectives

The tertiary exploratory objectives are to investigate the effect of tirzepatide 5 mg, 10 mg, or 15 mg SC QW versus placebo for:

- Additional histological measures with respect to mean change in the liver histology score from baseline for:
 - Expanded ballooning score
 - Expanded portal inflammation score
 - Expanded fibrosis Stage 1 scores
 - Mallory-Denk body score
 - Glycogenosis score

- Liver inflammation and fibrosis with respect to mean change from baseline in extracellular hepatic water content measured by iron-corrected T1 imaging (cT1, in ms) by MRI.
- Liver stiffness with respect to mean change from baseline in liver stiffness (in kPa) measured by TE.
- Liver enzymes and serum biomarkers of NASH and fibrosis with respect to mean changes from baseline in ALT, AST, GGT, K-18, Pro-C3, ELF, FIB-4, Adiponectin, Leptin, and Ferritin.
- Insulin sensitivity with respect to mean changes from baseline in fasting insulin and HOMA-IR.
- Decreasing waist circumference with respect to mean change from baseline in waist circumference (centimeters).
- PROs with respect to changes from baseline in:
 - PROMIS Fatigue short form 8a v1.0 score
 - PROMIS Pain Interference short form 4a v1.0 score
 - CLDQ-NAFLD total and domain scores
 - PGIS
- NASH resolution from baseline based on overall assessment of histology by pathologists.
- Decreasing NAS with respect to mean change from baseline in NAS on liver histology.
- Decreasing steatosis, hepatocellular ballooning, or lobular inflammation with respect to mean change from baseline in the liver histology score for:
 - Steatosis
 - Hepatocellular ballooning
 - Lobular inflammation
- Decreasing steatosis, hepatocellular ballooning, or lobular inflammation by ≥ 1 point with respect to proportion of participants that achieve a ≥ 1 -point improvement in the liver histology score from baseline for:
 - Steatosis
 - Hepatocellular ballooning
 - Lobular inflammation
- Decreasing fibrosis stage with respect to mean change from baseline in fibrosis stage on liver histology.
- Regression of fibrosis with no worsening of NASH with respect to proportion of participants with ≥ 2 -point decrease from baseline in fibrosis stage, and no worsening of NASH on liver histology.

- Prevention of progression to cirrhosis with respect to proportion of participants classified with cirrhosis (F4) on liver histology.

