3.2. General Considerations

Statistical analysis of this study will be the responsibility of Eli Lilly and Company (Lilly) or its designee. All statistical analyses will be conducted with SAS Version 9.4 or higher unless otherwise stated. Some analyses and summaries described in this analysis plan may not be conducted if not warranted by data (e.g., few events to justify conducting an analysis). Listings of events will be provided in such situations. Additional analyses of the data may be conducted as deemed appropriate without further changes made to the protocol or SAP, even after the primary or final database locks.

Additionally, to avoid potential selection biases, unless stated otherwise, statistical summaries and analyses will be conducted based on randomized study treatment group regardless of the actual treatment received by the patient. Unless otherwise noted, all tests of treatment effects will be conducted at a 2-sided alpha level of 0.05, and the CI will be calculated at 95%, 2-sided. In statistical summaries and analyses, patients will be analyzed as randomized.

For histological, imaging, and TE measurements the last available data during Visit 1 to Visit 3 prior to or within 1 week after the first study drug administration will serve as baseline. For patients who have an eligible historical biopsy within 6 months of Visit 1, the historical biopsy will serve as baseline for histological measures. Unless specified otherwise, the last measurement during Visit 1 to Visit 3 (including unscheduled visits) collected prior to or on the first dose day will serve as baseline. For immunogenicity, data collected up to the first dose time will serve as baseline. For laboratory and ECG, baseline needs to be prior to or within 1 hour after the first dose time. For PROs, data collected at Visit 3, regardless of the timing relative to the first dose, will serve as baseline.

There will be 2 estimands of interest in evaluating the primary and secondary efficacy objectives. The first estimand, the “efficacy” estimand, represents efficacy prior to discontinuation of study drug.

Primary Estimand (efficacy estimand)

The primary clinical question of interest is: What is the treatment difference in NASH resolution without worsening of fibrosis after 52 weeks of treatment assuming all participants who meet the inclusion criteria would have completed the treatment period?

The “efficacy estimand” is described by the following attributes:

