3.3. Adjustments for Covariates

The study is stratified based on T2DM status (Yes or No) at randomization and the region (Japan, US including Mexico, and Europe including Israel).

For efficacy-related analyses of histological endpoints, region and T2DM status at randomization will be used as covariates. Unless otherwise specified, for efficacy analyses of continuous measurements including non-histological and laboratory biomarkers, corresponding baseline value will be used as an additional covariate to T2DM status and the region.

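### ALT, AST, GGT and FIB-4 are scheduled twice before the first dose, but the SAP model adjusts only for the last value, so some precision on these exploratory endpoints may be lost (roughly 0% to 25% in equivalent sample size).

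*SAP*

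**What the plan says.** The Schedule of Activities (Protocol 1.3) marks the chemistry panel and FIB-4 at Visit 1 (nominally Week -6) and Visit 3 (Week 0). Protocol Appendix 2 places ALT, AST and GGT in the chemistry panel. A footnote to the schedule requires all screening and baseline procedures to be finished before the first dose.

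SAP 1.3 names the objective: "Liver enzymes and serum biomarkers of NASH and fibrosis with respect to mean changes from baseline in ALT, AST, GGT", followed by other markers that include FIB-4. Table GPHR.3.2 sends these markers to the mixed model of SAP 3.11.2.1, with ALT, AST and GGT on the log scale. That model has treatment, visit, their interaction, diabetes status, region and one baseline value of the outcome.

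The general baseline rule in SAP 3.2 is that "the last measurement during Visit 1 to Visit 3 (including unscheduled visits) collected prior to or on the first dose day will serve as baseline". The same section adds a timing limit for laboratory values relative to the first dose, and SAP 3.14.4 again takes the last non-missing pre-dose value. SAP 3.3 says that the "corresponding baseline value will be used as an additional covariate to T2DM status and the region". Nothing brings the Visit 1 value into the model when a later pre-dose value exists.

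For liver safety only, Protocol 8.2.4.2 uses a different baseline: "Baseline ALT is derived from an average of 2 pretreatment ALT measurements at least 2 weeks apart".

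**The concern.** A single laboratory value is an imperfect measure of a participant's underlying level. Protocol 8.2.4.2 itself notes that ALT fluctuates in the natural course of NASH. A second pre-dose value, already collected, can explain outcome variance that the first leaves over. If it is ignored, intervals for the enzyme and FIB-4 comparisons are wider than the data require.

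The arms are small: Protocol 9.2 says "assuming a 20% dropout rate, this results in approximately 40 completers per arm". Protocol 4.2 gives the noninvasive markers a purpose beyond description, namely developing future alternatives to liver biopsy. What is at stake is precision on exploratory endpoints, not validity.

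**Working it through.** **The plan's own figure.** The documents state no power, standard deviation or correlation for ALT, AST, GGT or FIB-4. The only sample-size statement concerns histology: a "2-sided significance level of 0.05 using a test of 2 proportions", rates of 42.5% and 12.5%, and at least 80% power. It reproduces. 196 × 0.8 / 4 = 39.2 completers per arm. At 39 to 40 per arm, power is 86% to 87% by the normal approximation and 81% to 82% by Fisher's exact test. It has no bearing on the markers except to fix the arm size.

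**Set-up.** Scale each value to variance 1. Let r3 and r1 be the correlations of the Visit 3 and Visit 1 values with a follow-up value, and r0 the correlation between the two pre-dose values. All three are assumptions. The residual variances are:

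- last value only: 1 − r3²
- simple mean of the two: 1 − [(r3 + r1)/2]² / [(1 + r0)/2]
- both entered: 1 − (r3² + r1² − 2·r1·r3·r0) / (1 − r0²)

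The gain in equivalent sample size is the first variance divided by the second or third, minus 1.

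**Equal correlations (r1 = r3 = r0 = ρ).** The mean and both-entered versions coincide, and the ratio is (1 + ρ)² / (1 + 2ρ).

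| ρ | Last only | Both | Gain |
|---|---|---|---|
| 0.5 | 0.750 | 0.667 | 12.5% |
| 0.6 | 0.640 | 0.550 | 16.4% |
| 0.7 | 0.510 | 0.424 | 20.4% |
| 0.8 | 0.360 | 0.289 | 24.6% |

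At ρ = 0.5 to 0.7 the interval width shrinks by a factor of √(1/1.125) = 0.94 to √(1/1.204) = 0.91, that is, by about 6% to 9%.

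**Pre-dose values closer to each other than to follow-up (r1 = r3 = r).** This is plausible: the visits are nominally 6 weeks apart, while follow-up runs to Week 52 on treatment.

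| r0 | r | Gain |
|---|---|---|
| 0.7 | 0.5 | 6.2% |
| 0.7 | 0.6 | 11.0% |
| 0.8 | 0.5 | 3.8% |
| 0.8 | 0.6 | 6.7% |
| 0.8 | 0.7 | 12.0% |

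**Visit 1 also a weaker predictor than Visit 3.**

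| r3 | r1 | r0 | Simple mean | Both entered |
|---|---|---|---|---|
| 0.6 | 0.55 | 0.7 | +4.7% | +5.5% |
| 0.7 | 0.65 | 0.8 | +3.3% | +4.6% |
| 0.7 | 0.56 | 0.8 | −8.8% | 0% |

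In the last row r1 = r3 × r0, so Visit 1 predicts follow-up only through Visit 3. Last only leaves 1 − 0.49 = 0.510. The simple mean leaves 1 − 0.63²/0.9 = 0.559, which is worse. Entering both leaves 0.510 and loses nothing but the degree of freedom.

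**Entry cuts for AST.** Participants who need a screening biopsy must have AST above 23 U/L (Protocol 5.1, criterion 5b). Selecting on the Visit 1 value weakens its use as a predictor. Simulation with equal correlations of 0.5 to 0.7 before the cut, an assumed log-scale SD of 0.45 and an assumed median of 25 to 35 U/L gives an AST gain of about 6% to 16%, instead of 12.5% to 20.4%.

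Those with a reliable FibroScan must also have a FAST score above 0.35. Since ln(0.35/0.65) = −0.619, the formula in Protocol 8.1.3.3.1 at LSM 8 kPa and CAP 300 dB/m gives −1.65 + 2.225 + 0.718 = 1.293. So 63.3/AST must be below 1.912, that is, AST above about 33 U/L. At LSM 10 kPa and CAP 320 dB/m the limit is about 27.5 U/L. With a cut at 33 U/L and correlations of 0.5 to 0.8, the simulated AST gain is about 7% to 18% (assumed median 42 U/L) or 5% to 14% (30 U/L).

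**The case against.** The last pre-dose value is a standard, valid covariate and gives an unbiased comparison. These endpoints are exploratory in a phase 2 trial, the sample size rests on histology, and SAP 3.2 allows additional analyses without amending the plan. All of this stands, and it sets the priority.

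The gain also depends on a correlation structure that nobody has stated. The SAP's mixed model does not presume equal correlation: it starts from an unstructured covariance and tries compound symmetry last. Visit 1 may be a poor guide. Screening can run to 12 weeks (Protocol 1.1). Users of DPP-4 inhibitors stop the drug before randomization, which for those with screening HbA1c at or below 8% comes about 3 months after screening (Protocol 5.4). FIB-4 is itself selected at both ends on the alternate biopsy route (above 1.3 and below 3.2), which the working does not model. This stands, and it is why the range reaches down to 0%. The zero-gain case, however, requires the Visit 3 value to carry no visit-specific noise of its own, which fits poorly with the Protocol's remark that ALT fluctuates.

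Two stronger readings are tempting. A reader might infer a firm loss of 10% to 22%. With equal correlations that needs a common value of about 0.43 to 0.74, which no document gives. A reader might also infer from Protocol 8.2.4.2 that the sponsor considers one ALT too noisy for a baseline. That section sets an individual reference for detecting possible drug-induced liver injury, and allows it to be reset to the nadir after a large fall. It makes no judgement on a covariate in a randomized comparison. It is an analogy, and there is no contradiction to reconcile.

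**Conclusion.** The point holds as a low-priority efficiency gain. Two scheduled pre-dose values exist, and the model uses one. Using both would be worth roughly 0% to 25% in equivalent sample size. The figure of about 12% to 20% applies only if all correlations are equal at 0.5 to 0.7. Fading correlation reduces the gain to about 0% to 12% in the cases examined, and for AST the entry cuts reduce it further. Every figure rests on assumed correlations and, for AST, on an assumed distribution. Neither the primary analysis nor the validity of the planned marker analysis is in question.

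**What to change.** In SAP 3.3 and in the ALT, AST, GGT and FIB-4 row of Table GPHR.3.2, keep the last pre-dose value as the reference for change. State that the Visit 1 and Visit 3 values are both entered as separate baseline covariates, on the log scale for ALT, AST and GGT. Do not substitute their simple mean, which lost about 9% in the fading-correlation case above. State what is done when only one pre-dose value is available, for example using that value for both covariates. Fix the wording before unblinding, so that the choice of covariates cannot be questioned later.

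The cost is one added covariate per marker, at most one degree of freedom, and a line or two of SAP text. No new samples, visits or changes to trial conduct are needed.

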1.4. Magnetic Resonance Elastography (MRE) Addendum Objectives

1.4.1. MRE Primary Objective

- The primary objective is to demonstrate that tirzepatide administered SC QW (pooled data from 5 mg, 10 mg, and 15 mg dose arms) is superior to placebo for the changes from baseline in liver stiffness as measured by 2-dimensional MRE at 52 weeks in participants with NASH.

1.4.2. MRE Secondary Objective

- The secondary objective is to compare tirzepatide, using data pooled from 5 mg, 10 mg, and 15 mg dosing arms, versus placebo on the relative change from baseline in liver stiffness as measured by 2-dimensional MRE at 52 weeks in participants with NASH.

1.4.3. MRE Exploratory Objectives

The exploratory objectives are:

- To compare each dose of tirzepatide (5 mg, 10 mg, and 15 mg) versus placebo on the change from baseline in liver stiffness measured by MRE at Week 26 and Week 52.
- To compare each dose of tirzepatide (5 mg, 10 mg, and 15 mg) versus placebo on the relative change from baseline in liver stiffness measured by MRE at Week 26 and Week 52.

Additional exploratory objectives are to evaluate for tirzepatide, pooled and/or for each individual dose, versus placebo in:

- The proportion of participants achieving $\geq 15\%$ reduction in liver stiffness from baseline.
- The proportion of participants with $\geq 15\%$ increase in liver stiffness from baseline.
- Among participants that achieve $\geq 15\%$ reduction in liver stiffness from baseline, the proportion of participants that achieve ≥ 1 stage regression of fibrosis on liver histology.
- Among participants with $\geq 15\%$ increase in liver stiffness from baseline, the proportion of participants with ≥ 1 stage worsening of fibrosis on liver histology.
- Among participants with $\geq 15\%$ decrease in liver stiffness from baseline, the proportion of participants achieving NASH resolution on liver histology.

The MRE primary and secondary objectives will also be assessed at Week 26.

2. Study Design

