- Population: participants who meet the inclusion criteria. Further details can be found in Section 5 of Protocol GPHR.
- Endpoint: NASH resolution without worsening of fibrosis at 52 weeks.
- Treatment condition: the randomized treatment.
- The ICE “permanent discontinuation of study drug” is handled by the hypothetical strategy and the potential outcome of interest is the response in the efficacy measurement if participants had adhered to the randomized treatment. There are no other defined ICES.
- Population-level summary: proportion of patients meet NASH resolution without worsening of fibrosis at Week 52.

Treatment effect of interest is thus defined as the difference in proportion of NASH resolution without worsening of fibrosis at Week 52 between QW LY3298176 (tirzepatide) and placebo. Rationale for “efficacy estimand”: This Phase 2 study aims to study the efficacy of LY3298176 (tirzepatide) under the ideal condition that all participants adhere to the randomized treatment. Data collected after the ICE will be set to missing.

Estimand(s) for Secondary Objectives

The same estimand for the primary objective will be used for the secondary efficacy endpoints for the secondary objectives.

Treatment-regimen estimand

The second estimand, the “treatment-regimen” estimand, represents the efficacy irrespective of adherence to investigational product and availability of the postbaseline biopsy. There are no ICE.

Unless specified otherwise, safety analyses will be conducted using the SS.

The end of study participation for a patient will be the earliest of date of death, date of withdrawal from further participation in the study, or date of the safety follow-up visit (Visit 801). For patients considered to be lost to follow-up, end of study participation will be the date of lost to follow-up reported by the investigator. Patient data included in the database after the last date of study participation (date of death, date of early termination or date of safety follow-up) will be excluded from statistical analyses. A listing of such data may be provided.

Summary statistics for categorical measures (including categorized continuous measures) will include sample size, frequency, and percentages. Summary statistics for continuous measures will include sample size, mean, SD, median, minimum, and maximum. The summary statistics

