3.11. Efficacy Analyses

The assessment of the primary, secondary and exploratory endpoints will be guided by the “efficacy” estimand. Analyses relative to the “efficacy” estimand will be conducted using the EAS without imputation of missing data. For exploratory purposes, and in the event of patients dropping out before Week 36, primary and key secondary efficacy analyses may be repeated using the EXAS guided by the “efficacy” estimand.

For informational purposes, the analysis of primary and key secondary endpoint may be repeated to be guided by the “treatment-regimen” estimand, which represents the efficacy irrespective of adherence to investigational product. Analyses relative to the “treatment-regimen” estimand will be conducted using the FAS. In this case, missing postbaseline measures will be imputed according to Section 3.11.1.3.

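### Three MRE exploratory objectives in SAP 1.4.3 set tirzepatide against placebo within subsets defined by stiffness change after randomisation; they should be worded as descriptive MRE-histology concordance by arm

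*SAP*

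**What the plan says.** In SAP 1.4.3 a single lead-in governs five bullets: "Additional exploratory objectives are to evaluate for tirzepatide, pooled and/or for each individual dose, versus placebo in". The first two bullets, the proportions with at least a 15% reduction and at least a 15% increase in stiffness, place no restriction on who is counted. The last three restrict the denominator:

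- among those with at least a 15% "reduction in liver stiffness from baseline, the proportion of participants that achieve" fibrosis regression of one stage or more;
- among those with at least a 15% "increase in liver stiffness from baseline, the proportion of participants with" fibrosis worsening of one stage or more;
- among those with at least a 15% "decrease in liver stiffness from baseline, the proportion of participants achieving NASH resolution on liver histology".

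Three other parts of the SAP bear on this. The MRE primary objective in 1.4.1 is to show that tirzepatide "is superior to placebo for the changes from baseline in liver stiffness as measured by 2-dimensional MRE at 52 weeks". Section 3.11 states: "The assessment of the primary, secondary and exploratory endpoints will be guided by the" efficacy estimand. Section 3.2 gives that estimand's first attribute: "Population: participants who meet the inclusion criteria".

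The version history says MRE objectives and analysis were added, but Table GPHR.3.2, which assigns a method to each exploratory outcome, has no MRE row. Nothing supplied labels the three items descriptive or defines an estimand for a subset formed by post-baseline response.

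**The concern.** Randomisation makes the arms comparable at baseline. It does not make stiffness responders on drug comparable with stiffness responders on placebo. If the drug lowers stiffness, the placebo participants who still reach a 15% fall are a more selected group than the drug participants who do. If stiffness and histology move together within an arm, that more selected group will also show more histological response, whatever the drug does to histology.

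Read as the lead-in has it, each of the three items is a treatment comparison in such a subset. A difference could be reported as a drug effect on histology, or its absence as a lack of effect, when it reflects who was selected. The population of the estimand that guides exploratory endpoints is set by the inclusion criteria, and these subsets do not match it.

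**Working it through.** **No plan figure to reproduce.** The documents give no sample size, rate or power for MRE. The one figure used from the plan is completers per arm (SAP 2.2): 196 × 0.8 / 4 = 39.2, which agrees with the stated figure of about 40.

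**Assumed inputs, none from the documents.** Percentage stiffness reduction is normal with mean 12 on drug and 0 on placebo, SD 15. Histological response is 26.8% in both arms, so there is no drug effect on histology. Within each arm, stiffness and a latent histology score are bivariate normal with correlation ρ.

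**Who enters the reduction subset**, P = Φ((mean − 15)/15):

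- drug: Φ(−0.2) = 42.1%, or 39.2 × 0.421 = 16.5 per dose arm;
- placebo: Φ(−1.0) = 15.9%, or 39.2 × 0.159 = 6.2.

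**Response inside the subset**, P(response | reduction ≥15%) = Φ₂(z_s, z_h; ρ) / Φ(z_s). Here Φ₂ is the bivariate normal distribution function, z_s = −0.2 (drug) or −1.0 (placebo), and Φ(z_h) = 0.268.

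| ρ | Drug | Placebo | Difference (points) |
|---|---|---|---|
| 0.2 | 33.0% | 37.5% | −4.5 |
| 0.3 | 36.2% | 43.3% | −7.1 |
| 0.4 | 39.6% | 49.6% | −10.0 |

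The true difference is zero in every row. The spurious difference vanishes if ρ = 0, or if the drug does not shift stiffness so that z_s is the same in both arms.

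**Other assumed rates.** With 30% histological response in both arms and a stiffness-responder rate raised from 20% to 50%, the differences are −7, −13 and −21 points at ρ = 0.3, 0.5 and 0.7. With a real 30-point effect (12.5% to 42.5%, the main trial's planning rates for NASH resolution without fibrosis worsening) and the same stiffness rates, the conditional difference is 29.5 points at ρ = 0.3 and 22.3 at ρ = 0.9.

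**The increase subset.** P(increase ≥15%) is Φ((−15 − 12)/15) = Φ(−1.8) = 3.6% on drug and Φ(−1.0) = 15.9% on placebo. That is 39.2 × 0.036 = 1.4 per dose arm against 6.2 on placebo.

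**Sampling error.** For one dose against placebo at ρ = 0.2, SE = √(0.330 × 0.670/16.5 + 0.375 × 0.625/6.2) = √(0.0134 + 0.0378) = 22.6 points, assuming every completer has MRE.

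**Two alternatives checked.**

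- *Crude pooling over arms.* Assume 40 placebo and 120 drug completers, responder rates of 20% and 50%, histology rates of 12.5% and 42.5%, and no association within either arm. Among stiffness responders, (8 × 0.125 + 60 × 0.425)/68 = 26.5/68 = 39.0%. Among non-responders, (32 × 0.125 + 60 × 0.425)/92 = 29.5/92 = 32.1%. Pooling creates concordance that exists in neither arm.
- *Joint endpoint (stiffness fall and histological response), everyone in the denominator.* With no histology effect and ρ = 0.2, it is 0.421 × 0.330 = 13.9% on drug against 0.159 × 0.375 = 6.0% on placebo. That 8-point gap comes from stiffness alone.

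**The case against.** The strongest reply is that these items are meant as biomarker concordance. The proportion with histological response among MRE responders, shown by arm, is the arm-specific positive predictive value. Setting tirzepatide beside placebo asks whether MRE tracks histology equally well in both. Protocol 4.2 gives developing alternatives to biopsy as an aim of the noninvasive measures. The lead-in says evaluate, whereas the two objectives before it say compare, and no test is named. All of this stands. A reader might infer that the three proportions answer no useful question, or that the SAP commits to a formal biased test; the documents support neither. What remains is the wording. The lead-in still evaluates drug against placebo, SAP 3.2 makes comparison with placebo the general rule, and nothing supplied says these items are exempt.

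The size also deserves caution. Every illustration rests on assumed rates, and the bias is small beside a standard error above 20 points. SAP 3.2 lets analyses be dropped when data are too few. The section heading points to an MRE addendum that is not among the documents and may settle the matter.

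**Conclusion.** The point holds as a wording fault with a real mechanism. As written, three exploratory objectives invite a non-randomised contrast in subsets that the drug is expected to select. With no histology effect, and under the assumed stiffness shift, the contrast is off by 4.5 to 10 points against the drug for correlations of 0.2 to 0.4. It is zero if stiffness is not shifted or is unrelated to histology within arms. The mechanism does not depend on the particular numbers, but the size does. No single figure should be quoted as the bias in this trial.

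A reader might infer that the trial's efficacy conclusions are at risk. They are not: these are additional exploratory objectives, no multiplicity control applies (SAP 3.6), and no primary or secondary conclusion, sample size or decision rule draws on them. The first two bullets under the same lead-in are ordinary between-arm comparisons and are unaffected.

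**What to change.** Move the three restricted bullets out of the lead-in that compares with placebo. Give them their own sentence stating that they describe concordance between MRE change and histological change. Report each proportion with its denominator and a confidence interval by treatment arm, with no between-arm test and no treatment-effect interpretation.

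If one overall figure is wanted, stratify it by arm; crude pooling mixes in the treatment effect. Do not present a joint stiffness-and-histology endpoint as a histology effect, because it can differ through stiffness alone.

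The cost is SAP wording only. The one thing given up is inference: the arm-specific conditional proportions become descriptive. If the MRE addendum already says this, a cross-reference in 1.4.3 is enough.
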